TITLE PAGE

Protocol for non-interventional studies based on existing data

Document Number:	<document number>
BI Study Number:	CTMS 1200.335
BI Investigational Product(s):	Gilotrif® (afatinib)
Title:	Assessment of Real-World Outcomes Associated with Afatinib (Gilotrif) Use in Patients with Solid Tumors Harboring NRG1 Gene Fusions
Protocol version identifier:	v1.0
Date of last version of protocol:	N/A
PASS:	No
EU PAS register number:	
Active substance:	Afatinib Antineoplastic agents, tyrosine kinase inhibitors ATC code: L01XE13
Medicinal product:	Gilotrif 40 mg, 30 mg, 20 mg
Product reference:	20 mg: NDC: 0597-0141-30 30 mg: NDC: 0597-0137-30 40 mg: NDC: 0597-0138-30
Procedure number:	
Joint PASS:	
Research question and objectives:	
Research Questions:
 
 1. What are the characteristics of patients with NRG1 gene fusion-positive solid tumors treated with afatinib, and what are the characteristics of those treated with another systemic therapy? 
Study Objectives:
 
 1. To describe the demographic and clinical characteristics of patients with NRG1 gene fusion-positive solid tumors treated with afatinib and of patients with NRG1 gene fusion-positive solid tumors treated with other systemic therapy.

Proprietary confidential information © 2020 Boehringer Ingelheim International GmbH or one or more of its affiliated companies

	
2. To calculate the ORR and DOR among patients with NRG1 gene fusion-positive solid tumors treated with afatinib and among patients with NRG1 gene fusion-positive solid tumors treated with other systemic therapy3. To estimate PFS (and TOT, TTP) among patients with NRG1 gene fusion-positive solid tumors treated with afatinib and among patients with NRG1 gene fusions treated with other systemic therapy4. To estimate OS among patients with NRG1 gene fusion-positive solid tumors treated with afatinib and among patients with NRG1 gene fusion-positive solid tumors treated with other systemic therapy5. To describe the incidence and severity of adverse events (AEs) among patients with NRG1 gene fusion-positive solid tumors while on treatment with afatinib or other systemic therapy
Country(-ies) of study:	United States
Authors:	
Marketing authorization holder(s):	
MAH contact person:	
Date:	8-MAY-2020
Page 2 of 45	
Proprietary confidential information	

2. LIST OF ABBREVIATIONS

1L	First-line (therapy)
AACR	American Association for Cancer Research
ADR	Adverse drug reaction
AE	Adverse event
ALT	Alanine Aminotransferase
AST	Aspartate aminotransferase
BI	Boehringer Ingelheim Pharmaceuticals
CI	Confidence interval
CR	Complete response
CTCAE	Common Terminology Criteria for Adverse Event
Del19	exon 19 deletion mutation
DOCB	Duration of clinical benefit
DOR	Duration of response
ECOG PS	Eastern Cooperative Oncology Group Performance Status
eCRF	Electronic Case Report Form
EGF	Epidermal growth factor
EGFR	Epidermal growth factor receptor
EGFR+	EGFR mutation-positive
EHR	Electronic Health Record
EMR	Electronic Medical Record
FAE	Fatal adverse event
FDA	United States Food & Drug Administration
HIPAA	Health Insurance Portability and Accountability Act
HER2	human epidermal growth factor receptor-2
HER3	human epidermal growth factor receptor-3
IMA	Invasive mucinous adenocarcinoma
IRB	Institutional Review Board
ISPE	International Society for Pharmacoepidemiology
L858R	exon 21 point mutation
MMR	Mismatch Repair Genes
MSI	Microsatellite Instable
NIS	Non-interventional study
NSCLC	Non-small cell lung cancer
NRG1	Neuregulin-1
ORR	Overall response rate
OS	Overall survival
PHI	Protected Health Information
PFS	Progression-free survival
PD	Progressive disease
PR	Partial response
PS	Performance Status

[figure not shown]
RECIST	Response Evaluation Criteria In Solid Tumors
RCT	Randomized controlled trial
RWE	Real-world evidence
SAE	Serious adverse event
SD	Stable disease
SE	Standard Error
SJS	Stevens Johnson Syndrome
STROBE	Strengthening the Reporting of Observational Studies in Epidemiology
TEN	Toxic Epidermal Necrolysis
TKI	Tyrosine kinase inhibitor
TOT	Time on treatment
TTF	Time to treatment failure
TPP	Time to progression
US	United States

4. ABSTRACT

Name of company:			
Boehringer Ingelheim			
Name of finished medicinal product: Gilotrif®			
Name of active ingredient: afatinib Antineoplastic agents, tyrosine kinase inhibitors ATC code: L01XE13			
Protocol date: 17 March 2020	Study number: CTMS 1200.335	Version/Revision: 1.0	Version/Revision date: 17 March 2020
Title of study:	Assessment of Real-World Outcomes Associated with Afatinib (Gilotrif) Use in Patients with Solid Tumors Harboring NRG1 Gene Fusions		
Rationale and background:	
The first neuregulin 1 (NRG1) fusion was reported by Fernandez-Cuesta et al in 2014 when they identified five CD74-NRG1 fusions in invasive mucinous adenocarcinoma (IMA). Multiple tumor types with NRG1 fusions have been described, including other lung, renal, head and neck, pancreatic, breast, ovarian, uterine, and prostate. The CD74-NRG1 fusion provides an extracellular anchor for the epidermal growth factor (EGF) domain of NRG1 to bind to ErbB3 (HER3), leading to HER3 heterodimerization and activation of downstream signaling pathways resulting in oncogenesis. As such, targeted treatment with inhibitors of this pathway represents a possible therapeutic strategy. Afatinib, a pan-ErbB inhibitor, has been evaluated in preclinical models and in several case reports in patients with tumors harboring NRG1 fusions who have achieved durable benefit with afatinib. NRG1 fusions are rare, with an estimated overall frequency of ~0.2% to 0.8% across solid tumors and have a reported prevalence of up to 31% in lung IMA, making prospective clinical trials challenging.
 
Obtaining real-world data describing the real-world outcomes associated with afatinib in patients with NRG1 fusion-positive solid tumors is valuable, and such data may be used in supplemental applications for label expansion requests to the U.S. FDA and other agencies.
		

Research question and objectives:	
Research Questions:
 
1. What are the characteristics of patients with NRG1 gene fusion-positive solid tumors treated with afatinib, and what are the characteristics of those treated with another systemic therapy? 
Study Objectives:
 
1. To describe the demographic and clinical characteristics of patients with NRG1 gene fusion-positive solid tumors treated with afatinib and of patients with NRG1 gene fusion-positive solid tumors treated with other systemic therapy.2. To calculate the ORR and DOR among patients with NRG1 gene fusion-positive solid tumors treated with afatinib and among patients with NRG1 gene fusion-positive solid tumors treated with other systemic therapy3. To estimate PFS (and TOT, TTP) among patients with NRG1 gene fusion-positive solid tumors treated with afatinib and among patients with NRG1 gene fusions treated with other systemic therapy4. To estimate OS among patients with NRG1 gene fusion-positive solid tumors treated with afatinib and among patients with NRG1 gene fusion-positive solid tumors treated with other systemic therapy5. To describe the incidence and severity of adverse events (AEs) among patients with NRG1 gene fusion-positive solid tumors while on treatment with afatinib or other systemic therapy
Study design:	This retrospective cohort study will be conducted via a multi-site medical chart review of patients with NRG1 gene fusion-positive solid tumors. Two cohorts of patients will be identified: the first includes any patient with NRG1 gene fusion-positive solid tumors who has received afatinib in any line of therapy (afatinib cohort). The second includes any patient with NRG1 gene fusion-positive solid tumors who has not received afatinib in any line of therapy (other systemic therapy cohort). All patients must have initiated treatment after 01/01/2017 and before 03/31/2020. To remove potential bias, patients who died prior to 3 months following treatment initiation are still eligible. Data collection is anticipated to occur in Q3/Q4 of 2020, allowing for a minimum follow-up of approximately 3 months. Demographics, clinical characteristics, safety, and clinical outcomes (ORR, DOR, DOCB, TOT, TTP, PFS, OS, and AEs will be described for both patient cohorts.

Population:	Inclusion Criteria 
• Adults, 18 years of age or older, at the time of diagnosis with any solid tumor.• Confirmed NRG1 gene fusion in any solid tumor.• Initiated afatinib or other systemic therapy (in any line of therapy) for treatment of a solid tumor with NRG1 gene fusion on or after 01/01/2017 and before 03/31/2020.• Followed up for ≥ 3 months after initiation of afatinib or other systemic therapy (unless deceased prior to 3 months of follow-up). Exclusion Criteria 
• Treatment with any TKI/ErbB-directed therapy other than afatinib
Variables:	The primary exposure of interest is treatment with afatinib. Two unmatched cohorts of patients will be created: the afatinib-treated cohort includes patients with an NRG1 gene fusion who received afatinib in any line of therapy; the second cohort includes any patient with an NRG1 gene fusion who had never received afatinib prior to the date of data collection. Demographic and clinical characteristics (e.g., sex, age, payer type, US region, race/ethnicity, tumor type/characteristics, comorbidities, ECOG PS, NRG1 gene fusion testing [e.g., timing, lab/location, results/partner], tumor-specific testing of interest [e.g., EGFR]) will be described in each cohort of patients. Clinical outcomes to be measured in this study include ORR, DOR, DOCB, TOT, TTP, PFS, OS, and AEs.

Data sources:	
De-identified, patient-level data will be obtained from providers in the [REDACTED] who will complete an eCRF for eligible patients. [REDACTED] will recruit providers from [REDACTED] to participate. [REDACTED] is a community of over 7,000 oncologists, hematologists and urologists from across the U.S., with varying levels of time in practice, from practices both within and outside of group purchasing organizations. A subset of this provider group (~800) participates in retrospective observational research studies. All provider participation in the study is voluntary.
 
Providers will abstract clinical and treatment related data as available from the patient's EHR from the time of diagnosis of their primary malignancy through the last date of follow-up with the patient or death. Providers will complete an eCRF for all eligible patients and will begin data abstraction with the first eligible patients, subsequently selecting consecutive patients moving forward. Required data elements are specified in the study inclusion/exclusion criteria; non-required data elements may be missing/unknown. Providers may abstract data into the eCRF for both patients they personally managed/treated or those managed/treated by other providers within their practice.
 
Providers are compensated for their time completing data abstraction into the eCRF only after subsequent data verification, as necessary. No source documents will be provided to [REDACTED] for verification; however, [REDACTED] will require duplicate data entry for a sample of patients' initial data collection to verify data point accuracy.

----------------------	--

Study size:

The total target number of patients is up to 120 patients, including up to 70 patients with an *NRG1* gene fusion-positive solid tumor treated with afatinib and up to 50 patients with an *NRG1* gene fusion-positive solid tumor who had not received afatinib at the time of data collection. The target number of patients was based on the results of a pilot feasibility study conducted by [REDACTED] with Boehringer Ingelheim (BI).

In December 2019, [REDACTED] conducted outreach to approximately 800 providers in [REDACTED] to inquire as to the number of patients with *NRG1* gene fusion-positive solid tumors treated with afatinib whom they had personally managed or who were cared for at their practice. Providers were presented with similar inclusion criteria as those described above. In total, 12 oncologists completed short eCRFs describing a total of 108 patients. Of those, 67 (62%) were treated with afatinib and 41 (38%) had not received afatinib.

Based on the feasibility study, [REDACTED] will target up to 70 afatinib-treated patients with *NRG1* gene fusion-positive solid tumors and up to 50 patients with *NRG1* gene fusion-positive solid tumors who had not received afatinib. Although the feasibility study did not identify this number of patients, further recruitment of non-responders to the survey invitation will be used to achieve the target number of patients planned for this study. In lieu of a comparative analysis between the afatinib-treated and non-afatinib treated patients are exploratory, the precision of estimates involving 70 patients in the afatinib-treated cohort would be associated with a standard error of any bivariate response variable between 6.0% and 13.9%.

Data analysis:	
Demographic and clinical characteristics will be reported via descriptive analyses, including counts and frequencies for dichotomous and categorical variables, while measures of centrality (mean, median) and spread (min, max, standard deviation, interquartile range, as appropriate) will be used for continuous variables. These characteristics will be described at the time of initial diagnosis of advance/metastatic disease and at the time of initiation of each line of therapy received.
																						
	
For disease response, the point estimate for ORR and associated 95% confidence interval will be calculated for each cohort. The Kaplan-Meier method will be used to estimate any time to event outcome including DOR, DOCB, TOT, TTP, PFS, and OS to account for any right censoring (e.g., patient had not discontinued therapy, patient had not progressed or died).
																						
	
Given the small number of patients targeted for study inclusion and anticipated differences in baseline characteristics between afatinib-treated and patients treated with other systemic therapies, statistical comparisons are not planned. In lieu of statistical comparisons between cohorts, the non-afatinib cohort will provide context for interpreting results among those treated with afatinib. Specifically, this context includes what patients with NRG1 gene fusions not treated with afatinib look like, how they are managed and treated, and what their clinical outcomes look like. The non-afatinib cohort will provide a broader understanding of NRG1 gene fusions among patients with solid tumors, for which limited evidence currently exists.
																						
	
Incidence and severity of AEs will be summarized and displayed in number/percentage. All safety endpoints will be analysed descriptively.
																						
Milestones:	
  
 Task	Start Date	
   
 Internal approval of study synopsis	March 2020	
 
 Internal approval of study protocol	May 2020	
 
 Submission of study protocol to FDA	May 2020	
 
 FDA feedback received	June 2020	
 
 Finalization of protocol	July 2020	
 
 IRB submission and review	July 2020	
 
 Recruitment & data collection	Q3/Q4 2020	
 
 Demographics & clinical characteristics	November 2020	
 
 Outcomes assessment	November 2020	
 
 Final report	December 2020	
  
	Task	Start Date	Internal approval of study synopsis	March 2020	Internal approval of study protocol	May 2020	Submission of study protocol to FDA	May 2020	FDA feedback received	June 2020	Finalization of protocol	July 2020	IRB submission and review	July 2020	Recruitment & data collection	Q3/Q4 2020	Demographics & clinical characteristics	November 2020	Outcomes assessment	November 2020	Final report	December 2020
Task	Start Date																						
Internal approval of study synopsis	March 2020																						
Internal approval of study protocol	May 2020																						
Submission of study protocol to FDA	May 2020																						
FDA feedback received	June 2020																						
Finalization of protocol	July 2020																						
IRB submission and review	July 2020																						
Recruitment & data collection	Q3/Q4 2020																						
Demographics & clinical characteristics	November 2020																						
Outcomes assessment	November 2020																						
Final report	December 2020																						

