9.2 SETTING

Approximately 20 or more unique providers will participate in this research study. To minimize potential bias, the maximum number of patients each provider may select and complete data abstraction for is capped at 30; for any provider who submits >10 patients, their data will be reviewed in detail by a clinician and analyst to identify any data quality issues (see Section **9.8.2 Data Validation** for further details on data quality assurance and control measures). Data

will be collected through an electronic case report form (eCRF) completed by the patients' providers who volunteer to participate in the study. Providers will be compensated at fair market value for the time to complete data abstraction and quality control procedures, which are estimated to take up to 1 hour per patient.

Recruitment of providers will be conducted electronically. Providers who responded to an initial feasibility request and reported treating potentially eligible patients will be contacted and invited to participate. Recruitment to fill the up-to-120-patient quota will run for 4 weeks from the date of recruitment launch. During that time, the per-cohort quotas will be electronically monitored to ensure that the final number of patients achieves up to 70 patients with *NRG1* gene fusion-positive solid tumors treated with afatinib and up to 50 with an *NRG1* gene fusion-positive solid tumor not treated with afatinib at the time of data collection. As recruitment for a cohort is completed, no further patient data entry will be allowed for that cohort; however, providers actively completing an eCRF at the time of quota close for a cohort will be allowed to complete that eCRF, and the total number of patients per cohort may exceed the quotas.

Providers will be asked to identify all eligible patients, and starting with the earliest index date, chronologically select consecutive patients meeting the eligibility criteria and complete the data abstraction. The eCRF is structured to allow data collection regarding patient clinical history at the time of initial diagnosis of their solid tumor, initiation of index therapy (including dates of dose starts, stops, and interruptions), response to therapy, dates of disease progression, AEs, (including dates of onset, recovery, and reported deaths).

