9.2.1 Provider/Site/Patient Selection

Provider Eligibility

Providers who meet the following criteria will be eligible to participate:

- 1) Are board-certified oncologist/hematologist.
- 2) Have treated/are treating at least one eligible patient with an *NRG1* fusion-positive solid tumor.
- 3) Are able to participate in research approved by an external institutional review board (IRB).
- 4) Agree to participate in data quality assurance/control processes.

Providers will select patients meeting the study eligibility criteria as described below. Providers will be asked to select eligible patients chronologically, starting with the first patient who first initiated any line of afatinib or chemotherapy, on or after 01/01/2017 through 03/31/2020.

Patient Eligibility

Inclusion Criteria:

- Adults, 18 years of age or older, at the time of diagnosis with any solid tumor.
- Confirmed *NRG1* gene fusion in any solid tumor.
- Initiated afatinib or other systemic therapy (in any line of therapy) for treatment of a solid tumor with *NRG1* gene fusion on or after 01/01/2017 through 03/31/2020.

- Followed up for ≥ 3 months after initiation of afatinib or other systemic therapy (unless deceased prior to 3 months of follow-up).

Exclusion Criteria:

- Treatment with any TKI/ErbB-directed therapy other than afatinib

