DOR	Duration of response will be calculated as the time from initial response (for any patient with a complete or partial response initially) until the earliest of either disease progression or death. Patients who discontinue therapy due to a reason other than progression will be censored on the date of discontinuation. Patients still on therapy at the time of data cut-off will be censored on their last visit date.
TOT	Time from initiation of a line of therapy until discontinuation for any reason; patients on therapy at the time of data cut-off will be censored on the last date of treatment.
TTP	Time from initiation of a line of therapy until discontinuation due to disease progression; patients on therapy or those who discontinued due to a reason other than disease progression will be censored on the last date of treatment.

PFS	Time from initiation of a line of therapy until disease progression or death; patients on therapy at the time of data cut-off will be censored on the last date of treatment. Patients who discontinue a line of therapy for a reason other than disease progression but who subsequently die prior to the receipt of any other therapy will be considered an event on the date of death.
OS	Time from initiation of any therapy in the metastatic setting until death; patients alive at the time of data cut-off will be censored on the last date the patient was seen by the provider/clinic.
AE	An adverse event is defined as any untoward medical occurrence in a patient administered a medicinal product and which does not necessarily have a causal relationship with this treatment. AEs from a prepopulated list (including “other, please specify”) during each line of therapy will be indicated by providers. The number and proportion of patients experiencing each AE reported during afatinib or other systemic therapy will be reported. See Section 11.1 and Table 3 for further details.

In addition to TOT, to further characterize treatment patterns for those treated with afatinib and those treated with other systemic therapy, the following will be collected (and calculated based on the collected data):

- Treatment history (i.e., regimens, duration, number of cycles, sequence)
- Starting dose of afatinib or other systemic therapy
- Dose modifications of afatinib or other systemic therapy (i.e., dose reductions and their timing, dose increases and their timing, dose delays and their duration and timing)

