9.12 BIAS

Provider and patient selection bias may exist in this study. Provider selection bias will be minimized by only allowing providers to contribute up to 30 patients each. It is expected, however, given the rarity of the patient profile included in this study, that the mean number of patients each provider will contribute is approximately 5 and the total number of providers participating will be greater than 20. Patient selection bias will be minimized to the extent possible by requesting providers complete eCRFs for eligible patients starting chronologically with the earliest patient meeting the criteria and selecting patients consecutively thereafter. To assess the degree of selection made by the participating provider, the total number of patients meeting the study selection criteria will be collected (e.g., 5 patients meet study inclusion/exclusion criteria) will be compared to the number of patients contributed to the study (e.g., 3 patients submitted as CRFs).

In addition, the extent of both provider and patient selection bias is likely minimized by the stringent study selection criteria. Because of the relative rarity of *NRG1* fusion-positive histology, the total prevalence of this patient population is likely small, minimizing potential selection biases.

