11 MANAGEMENT AND REPORTING OF ADVERSE EVENTS/ADVERSE REACTIONS

This is a retrospective, non-interventional, non-randomized study using data contained in structured and unstructured areas of the patients EHR previously collected as part of routine clinical care. We are asking chart abstractors (i.e., the patients' treating providers) to abstract information on AEs during afatinib or other systemic therapy. Reporting of these events will be conducted in the manner described in section 11.2.

In addition, reporting requirements and procedures for other AEs identified during the chart review are described in 11.2.

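### Patients whose index therapy was given in an interventional trial are neither excluded nor identified, so the real-world estimates can mix routine and trial care

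*Combined protocol and SAP*

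**What the plan says.** The Abstract (Section 4, Population) and Section 9.2.1 carry the same single exclusion: "Treatment with any TKI/ErbB-directed therapy other than afatinib". The inclusion criteria cover adult age, a confirmed fusion, an index start in the 2017 to 2020 window, and at least three months of follow-up unless the patient died. The treatment criterion reads "Initiated afatinib or other systemic therapy (in any line of therapy) for treatment of a solid tumor with" an NRG1 fusion. It sets no condition on where or how the drug was given.

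Section 11 describes the source as chart data "previously collected as part of routine clinical care". That describes the data; it is not an eligibility rule.

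Among listed variables, Table 1 has demographics, tumor, performance status, comorbidity, stage and biomarkers. The treatment-pattern items in Section 9.3.2 include "Treatment history (i.e., regimens, duration, number of cycles, sequence"), along with dosing and the reason for stopping. Trial participation is not listed. The analysis (9.7) and the limitations (9.9) do not mention it either.

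On sampling, Section 9.2 asks providers to "chronologically select consecutive patients meeting the eligibility criteria", starting from the earliest index date. Section 9.12 adds that "the total number of patients meeting the study selection criteria will be collected" and compared with the number submitted.

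**The concern.** A patient who received afatinib, or an agent that is neither a TKI nor ErbB-directed, inside an interventional trial can meet every criterion. This is plausible. Section 7 gives approved afatinib indications only within non-small cell lung cancer, whereas the study covers any solid tumor, so trial supply is one way in which such use could arise.

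Trial patients differ in ways that reach the endpoints. They pass a trial's entry criteria, and they are scanned on a fixed schedule. Section 9.3.2 takes response as charted together with the imaging date, and DOR, TTP and PFS all depend on recorded progression, so scan frequency affects them directly. For adverse events, Section 9.9 itself expects less complete capture in routine practice than in a controlled trial. Pooling the two therefore combines two levels of ascertainment.

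The background sections say the results may support label expansion. A reader of such a submission would take the estimates to describe routine care, and the plan as written does not secure that.

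**Working it through.** **Step 1. Is there a rule or a field?**

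| Place | Content | Trial participation covered? |
|---|---|---|
| Abstract and 9.2.1, exclusion | Other TKI/ErbB-directed therapy only | No |
| Abstract and 9.2.1, inclusion | Age, fusion, index window, follow-up | No |
| 9.3.2, Table 1 and treatment items | Characteristics, regimens, dosing, reason for stopping | No |
| 9.3.2, Tables 2 and 3 | Outcomes and adverse events | No |
| 9.7 and 9.9 | Subgroups by tumor and line, monotherapy; limitations | No |
| 11 | Source described as routine care | Descriptive only |

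**Step 2. How large could the effect on ORR be?** The plan gives cohort sizes of up to 70 (afatinib) and up to 50 (other systemic therapy). It gives neither the number k of trial-treated patients nor the difference d between their ORR and that of the rest. Both are assumed here: k = 5 to 10, d = 20 to 30 percentage points in either direction. With p the ORR in the routine-care patients,

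pooled ORR = [(n − k)p + k(p + d)]/n = p + (k/n)d,

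so the shift is (k/n)d and does not depend on p.

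| n | k=5, d=20 | k=5, d=30 | k=10, d=20 | k=10, d=30 |
|---|---|---|---|---|
| 70 | 5/70 × 20 = 1.4 | 2.1 | 2.9 | 10/70 × 30 = 4.3 |
| 50 | 5/50 × 20 = 2.0 | 3.0 | 4.0 | 10/50 × 30 = 6.0 |

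**Step 3. Set this against the plan's own precision.** Table 4 (Section 9.5) gives ±10.7% at n=70 and ±12.7% at n=50 for a proportion of 30%. Both reproduce as 95% half-widths: 1.96 × √(0.30 × 0.70/70) = 10.7% and 1.96 × √(0.30 × 0.70/50) = 12.7%. The illustrative shifts lie inside these half-widths. They are, however, a displacement of the estimate, which the confidence interval does not cover and which a larger sample does not reduce if the share k/n stays the same.

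**The case against.** The strongest reply is that few trial patients are likely. The fusion is rare, and the plan says this makes prospective trials difficult. The TKI/ErbB exclusion removes anyone given another agent of that kind, in a trial or not. Section 9.4 bars practices that require local IRB approval, which plausibly removes some trial-active sites. The study is also descriptive, with no hypothesis and no comparison of cohorts. All of this stands, and it narrows the problem. It does not close it: an afatinib trial, or a trial of another drug class in the second cohort, still qualifies.

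A reader might infer that trial patients could never be found afterwards. The documents do not support that. The eCRF is not among them, so a field there cannot be ruled out, and Section 9.8.2 gives each patient a code through which the provider can be contacted again. What is missing is a stated rule and a planned item.

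A reader might also infer that patients already published as responders inflate the afatinib ORR, since the rationale cites cases with tumors harboring "fusions who have achieved durable benefit with afatinib". One can calculate that 3, 5 or 7 such responders among 70, with 30% in the rest, give 33.0%, 35.0% or 37.0%. That arithmetic treats them as contaminants by assumption. Under consecutive selection, a responder who started in the window belongs in the ORR, published or not. Bias would require that a known response determined which providers volunteered or which patients were submitted, and the documents do not show this. The cited afatinib case reports date from 2017 and the window opens on 01/01/2017. Those patients' start dates are not given, so overlap is possible but not shown.

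**Conclusion.** The omission is confirmed. The plan claims routine-care data but has no criterion, listed variable or analysis that makes the claim operational for trial-treated patients. ORR, DOR, PFS, TTP and adverse event rates can therefore mix routine and trial care.

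The size is unknown. The 1.4 to 4.3 points (n=70) and 2 to 6 points (n=50) rest on assumed counts and assumed ORR differences, with no known sign. Nothing in the documents shows that any trial patient will enter the study. The point is that, under the stated plan, a reader of the results could not tell. It is worth correcting before data collection because the correction is cheap then and much harder once the anonymized dataset has been delivered (Section 10). The conclusion does not extend to prior publication as a source of demonstrated bias.

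**What to change.** Add one eCRF item to Section 9.3.2: index therapy received as part of an interventional clinical trial, yes or no. Make it a required field, because Section 9.4 allows non-required elements to be missing. Then choose one of two routes and state it in the Abstract, Section 9.2.1 and Section 9.7:

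- exclude patients answering yes; or
- to protect the small cohorts, keep them, report them separately, and give ORR and the time-to-event outcomes for each cohort with and without them.

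Prior publication of a patient's response may be recorded as a descriptive check on overlap with the background case reports. It should not be an exclusion. An ORR that leaves those patients out should not be presented as a corrected ORR, since dropping patients on a marker linked to response would bias it downward.

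The cost is one more required item, one more table, and possibly a few patients fewer in the main estimate. The publication check, if adopted, adds one further item.
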